Précis:	The STAR-Caregivers program is an education, training, and support intervention demonstrated efficacious in reducing the behavioral and psychological symptoms of dementia. The investigators propose to test a 6-session, self-directed, online version called STAR-virtual training and follow-up (STAR-VTF) that leverages secure email within the member portal at Kaiser Permanente Washington, an online learning management system, and 6 30-minute coaching telephone calls to improve access to training, fidelity to the STAR principles, and to lower the cost of the program. Outcomes in the intervention arm will be compared to an attention control group that receives printed materials and links to online training resources but does not receive coaching.
Objectives:	Test the effectiveness of the intervention training vs. attention control in a practical clinical trial involving one hundred caregiver-person living with dementia dyads at Kaiser Permanente Washington.
Populations:	Persons living with dementia and their informal caregivers (spouses and adult children)
Site:	Kaiser Permanente Washington
Description of Intervention:	This study evaluates the effectiveness of a caregiver outreach, self-directed online training, and support program for caregivers of people with dementia who are using an antipsychotic medication to manage agitation/aggression. The Investigators will conduct a randomized trial of the caregiver program compared to a control group to measure differences in caregiver burden and discontinuation of antipsychotic medication use. The results will help in expanding access to and delivery of empirically supported behavioral health services for caregivers and persons living with dementia.
Trial Duration:	18 months
Subject Participation Duration:	6 months
Estimated Time to Complete Enrollment:	12 months

2 INTRODUCTION: BACKGROUND INFORMATION AND SCIENTIFIC RATIONALE

2.1 *Background Information*

Alzheimer's Disease and related dementias (ADRD) are debilitating conditions affecting more than 5 million Americans in 2014.(1, 2) With aging of the population it is projected that 8.4 million people will be diagnosed with ADRD over the next 15 years(3, 4) and health care costs attributable to ADRD are projected to be more than 1.2 trillion by 2050.(2) Behavioral and Psychological Symptoms of Dementia (BPSD) (anxiety, agitation, depression) are common and often involve aggressive behavior towards family caregivers (CG) in response to unmet needs, discomfort, or frustration. BPSD are disturbing and frequently lead to CG seeking medication to control patient symptoms. Antipsychotic use in persons living with dementia (PLWD) more than doubles mortality risk;(5) however, many caregivers are willing to accept those risks. The Choosing Wisely Guidelines from the American Psychiatric Association(6) and American Geriatrics Society(7) both recommend against prescribing antipsychotics as a first-line treatment for BPSD. STAR-Caregivers is an efficacious first-line behavioral treatment, endorsed by the Administration on Aging,(8) that involves caregiver training to manage BPSD.(9-16) However, the program has not been implemented widely – partly due to the cost of the programs,(17) difficulty conducting outreach,(18, 19) and modality of training (in person with written materials). Adequate caregiver training and commensurate reduction in caregiver burden are the mediators (mechanisms) we will engage in this Stage III trial to reduce BPSD and discontinue antipsychotic medication use by PLWD.

2.2 *Rationale and Objectives*

The STAR-Caregivers program is an education, training, and support intervention demonstrated efficacious in reducing BPSD.(9, 10, 20, 21) The original program involved 8 face-to-face, in-home training sessions and 4 follow-up phone calls. The condensed version involves 4 in-home sessions with 2 phone follow-ups.(18) Neither of these is feasible from a payer perspective due to the cost and, more recently, the COVID-19 pandemic makes home visits risky. We will test a self-directed, online version called STAR-virtual training and follow-up (STAR-VTF) that leverages weekly telephone calls and secure email within the member portal at Kaiser Permanente Washington to improve access to training, fidelity to the STAR principles, and to lower the cost of the program.

This trial will ascertain the feasibility and acceptability of STAR-VTF in which (a) caregiver training materials are delivered electronically and learning is self-directed, (b) caregivers have 7 telephone calls with a social worker and (c) where caregivers receive ongoing support from a social worker via secure messaging in the web-based portal (My Kaiser Permanente). We will compare outcomes in the STAR-VTF group to an attention control group that receives mailed material from the Alzheimer's Association and National Institute of Mental Health plus generic secure messages. Our specific aims are:

AIM 1: Assess the feasibility and acceptability of conducting caregiver outreach, training, and support via social workers and licensed mental health counselors including: (1) willingness of caregivers to interact through secure messaging (contact rates) and telephone; and (2) willingness of caregivers to complete self-directed training (training completion rates).

AIM2: Assess the feasibility and acceptability of the program from the payer perspective including: (1) average time spent per orientation visit; (2) average time per month spent responding to caregiver emails and coordinating care with primary care physicians; and (3) differences in face-to-face primary care, urgent care, and emergency department visit rates by PLWD.

AIM 3: Test the hypotheses that (H1) caregiver participants in STAR-VTF will have lower levels of caregiver burden at 8 weeks and 6 months compared to an attention control group; and (H2) PLWD participants in STAR-VTF will have lower rates of antipsychotic medication use at 6 months compared to control. Secondary outcomes are: caregiver depression, caregiver stress and caregiver self-efficacy. We propose to recruit 100 CG-PLWD dyads (50 per arm).

This will be the first study to test a low intensity, self-directed caregiver training program with remote support from social workers. It will also be the first study to measure changes in antipsychotic medication use by PLWD after CG training. Kaiser Permanente is an ideal setting because we have access to the complete EHR, prescription medication use, health care use, and demographic data. We will be able to identify and enroll participants in real-time using an automated data algorithm as we have done previously.(22) This study will be an important step in expanding access to training and support in a format that could be implemented within integrated delivery systems with capitated payments (i.e., Accountable Care Organizations). Growing use of EHR portals in these organizations will further increase demand for web-based care management/support. Demand will also increase as today's near-retirees, familiar with web-based applications, develop ADRD. Kaiser Permanente has pioneered such efforts and is the lead site in the Mental Health Research Network (MHRN). Findings from this study will inform a future multi-site pragmatic trial across the 13 health systems and 12 million enrollees in the MHRN.

3 OUTCOME MEASURES

Outcome measures will be collected regardless of the extent to which intervention arm caregivers or families accepted or utilized interventional components. That is, we will follow an intent-to-treat approach and encouragement trial methods.

3.1 Primary Outcomes

The following primary quantitative outcome measures for the trial will be assessed for the grant deliverables:

- (1) **Change in caregiver burden at 8 weeks and 6 months.** Self-reported caregiver burden will be assessed by the Disruption subscale on the Revised Memory and Behavior Problem Checklist (RMBPC) questionnaire. The range in subscale scores is 0 to 32 with higher scores representing a worse outcome.

3.2 Secondary Outcomes

The following secondary outcome measures for the trial will be assessed:

- (1) **Antipsychotic medication Use.** Proportion of participants will at least one antipsychotic prescription refill after initial medication dispensing, using automated system pharmacy data.
- (2) **Change in caregiver depression.** Self-reported caregiver depression assessed by the 8-item Patient Health Questionnaire (PHQ-8). The PHQ-8 is an eight-item measure of depression that assesses symptoms over the last two weeks. The total sum of the 8 responses from the PHQ-8 ranges between 0 and 24 with higher scores indicating worse outcome. In general, a total of 10 or above is suggestive of the presence of depression.
- (3) **Change in caregiver self-efficacy.** Self-reported caregiver self-efficacy assessed by the Caregiver Mastery Scale. Total scores can range from 7 to 35, with higher scores reflecting greater caregiver mastery. The Caregiver Mastery Scale is a 7-item measure of self-efficacy. is a 7-item self-report scale, indicating the extent to which respondents agree (5) or disagree (1) with each item. Three items with negative statements are reverse-scored. Total scores can range from 7 to 35, with higher scores reflecting greater caregiver mastery.
- (4) **Change in caregiver stress.** Caregiver stress will be measured on the Kingston Caregiver Stress Scale. This is a 10-item measure with respondents rating the level of stress between 1 (coping fine, no stress) to 5 (extreme stress, feeling at the end of rope). Total scores vary between 10 and 50.
- (5) **Response rates for baseline, 8-week, and 6-month measures.** We will assess participants' willingness to complete study measures using the REDCap online survey by the proportion completing study measures at each time point.
- (6) **Training Completion rate.** We will report training completion rates as a measure of feasibility. Completion will be defined as viewing all 6 online training modules, conducting at least 3 phone calls with a study coach and sending at least one secure message to a study coach in the baseline to 8-week period and one message in weeks 9 through 24.
- (7) **Primary care visit rates.** Measured as the number of primary care visits per eligible study participant during the study period.

- (8) **Urgent care visit rates.** Measured as the number of urgent care visits per eligible study participant during the study period.
- (9) **Emergency department visit rates.** Measured as the number of emergency department care visits per eligible study participant during the study period.
- (10) **Case management time.** We will estimate the time spent responding to ad hoc secure messages and phone calls by caregivers in order to inform the feasibility of the intervention from a payer perspective.

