6 INTERVENTION ARM

6.1 *Intervention Arm*

Randomized PLWD-CG dyads are offered:

- A telephone orientation visit with a study coach to acquaint the caregiver to the 6-session STAR-VTF program and online learning environment.
- A paper-based and electronic manual to identify priority behaviors, develop plans for addressing behaviors, and make plans for pleasant events.
- 6 weekly telephone coaching visits lasting 30 minutes and corresponding to each of the 6 training modules.
- Secure message (email) support within the patient portal, as needed, with the coach to help with personalizing the STAR-VTF curriculum for up to 6 months, as initiated by the caregiver.

We anticipate that self-directed caregiver training with support from social workers will enhance caregivers' sense of competence and self-efficacy. Training caregivers on good communication and the ABCs of dementia problem-solving will lead to decreased activation of behavioral triggers, lower incidence of problem behaviors, and lower caregiver stress in response to behaviors. Assisting caregivers to engage in higher levels of pleasant activities will enhance PLWD and caregiver mood and create a more positive care environment. With increased insight into the natural disease history, caregivers will be able to reframe behaviors as symptoms of dementia rather than insensitivity, rudeness, or deliberate provocation. We hypothesize that changes in the physical and psychosocial environment that reduce triggering events and improve caregiver-PLWD dyadic interactions will reduce the need for and use of antipsychotic medication.

6.2 *Eligibility Confirmation*

Once a PLWD is identified using the automated algorithm, a REDCap database is populated with the potential participants once per week. There are three steps to confirming eligibility.

- A study staff person will review the PLWD medical record to confirm that the person has a diagnosis of ADRD, an emergency contact or other family/friend is listed in the record, and that the PLWD does not live in an adult family home, skilled nursing facility, or memory facility.
- If eligible after medical record review, the staff person will contact a study coach (clinician) who will send a staff message within the EHR to the physician who prescribed the antipsychotic medication to the PLWD. The prescribing clinician will be asked:
 - Is [PLWD] capable of making health care decisions for themselves? [YES/NO/SOMETIMES]

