6.7 Secure Messaging (Email in the patient portal)

Caregivers will be invited to communicate with their coach via email at the completion of the 6-week training program and up to the end of the 6-month follow-up period. Coaches will only respond to messages initiated by caregivers. Telephone support will be given only as necessary.

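### The training completion outcome also requires two secure messages that the program leaves optional, so some caregivers who finish the modules and calls count as non-completers

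*Protocol*

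**What the plan says.** Protocol section 3.2, outcome 6 (Training Completion rate), sets four conditions that must all be met. The first two are: "Completion will be defined as viewing all 6 online training modules, conducting at least 3 phone calls with a study coach". The other two follow in the same sentence: "sending at least one secure message to a study coach in the baseline to 8-week period and one message in weeks 9 through 24".

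The rest of the protocol treats these parts differently:

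- **Calls.** Section 6.1 schedules "6 weekly telephone coaching visits lasting 30 minutes and corresponding to each of the 6 training modules".
- **Messaging.** Section 6.1 offers "Secure message (email) support within the patient portal, as needed, with the coach", and makes it available "for up to 6 months, as initiated by the caregiver". Section 6.7 adds that coaches answer messages but do not start them, and says: "Caregivers will be invited to communicate with their coach via email at the completion of the 6-week training program".
- **Aim 1 (section 2.2).** Item (1) is willingness to be in contact by secure message and telephone, measured by contact rates. Item (2) is "willingness of caregivers to complete self-directed training (training completion rates".
- **Analysis.** Section 7.2.3 fits a logistic model to completion versus non-completion and gives no other definition. The SAP does not mention training completion.

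**The concern.** The outcome's name and Aim 1 item (2) both point to a measure of whether caregivers finish the self-directed training. The definition adds use of a service that caregivers need not use. The second message also falls in weeks 9 to 24, after a curriculum of six weekly modules is due to be over.

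A low rate would then have two explanations that the outcome cannot separate: caregivers gave up the training, or they finished it and had nothing to ask by message. The coaching calls already cover each module, and sections 3.2 (outcome 10) and 7.2.4 expect ad hoc phone calls too. A caregiver whose questions are settled by telephone has less reason to write and still fails the definition.

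Section 2.2 says the findings will inform a future multi-site trial. An understated rate could suggest there that caregivers will not complete self-directed training when they do. The section 7.2.3 model is affected as well, because its covariates would be predicting messaging behavior as well as completion.

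**Working it through.** **Is there a figure to reproduce?** No. The documents give no expected completion rate, messaging rate or completion threshold. The check is therefore logical first, with arithmetic only as illustration.

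**Step 1: apply the definition to cases.**

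| Modules viewed | Coach calls | Message, baseline to week 8 | Message, weeks 9 to 24 | Status under outcome 6 |
|---|---|---|---|---|
| 6 of 6 | 6 of 6 | yes | yes | completer |
| 6 of 6 | 6 of 6 | no | yes | non-completer |
| 6 of 6 | 6 of 6 | yes | no | non-completer |
| 6 of 6 | 6 of 6 | no | no | non-completer |
| 6 of 6 | 3 of 6 | yes | yes | completer |

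The second to fourth rows describe caregivers who received all the training and coaching on offer. The fifth had half the calls and is a completer. Nothing in section 7.2.3 or the SAP changes these classifications.

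**Step 2: a bound that needs no assumed rates.** All four conditions are required, so

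reported rate = P(modules and calls and message 1 and message 2) ≤ P(message 1 and message 2).

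Whatever the training adherence, the reported rate is capped by the share messaging in both windows. If, say, half of the 50 intervention caregivers did so, the rate could not exceed 25/50 = 50%, even with every module and call finished by everyone.

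**Step 3: illustration.** The denominator of 50 is the planned intervention arm (section 7.1). Everything else is assumed:

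- c = 0.80 is the share who view all six modules and have at least three calls, so 50 × 0.80 = 40 caregivers.
- m1 and m2 are the shares *of those 40* who message in the first and second windows.

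The number counted as completers is 40 × P(both messages). P(both) is m1 × m2 under independence. It is at least max(0, m1 + m2 − 1) and at most min(m1, m2).

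| m1 | m2 | Independent | Lowest overlap | Highest overlap |
|---|---|---|---|---|
| 0.9 | 0.9 | 40 × 0.81 = 32.4 (65%) | 40 × 0.8 = 32 (64%) | 40 × 0.9 = 36 (72%) |
| 0.7 | 0.7 | 40 × 0.49 = 19.6 (39%) | 40 × 0.4 = 16 (32%) | 40 × 0.7 = 28 (56%) |
| 0.5 | 0.5 | 40 × 0.25 = 10 (20%) | 0 (0%) | 40 × 0.5 = 20 (40%) |
| 0.7 | 0.3 | 40 × 0.21 = 8.4 (17%) | 0 (0%) | 40 × 0.3 = 12 (24%) |

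Percentages are of 50. With modules and calls alone, every row would read 40 (80%).

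**Step 4: attrition.** Section 7.1 allows for 10% lost by 6 months, or about 5 of 50 per arm if split evenly. A caregiver who finishes the training and leaves before sending a message in weeks 9 to 24 becomes a training non-completer.

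**The case against.** The best defense is that the composite is deliberate. It is explicit and prespecified. The program is training plus follow-up, section 2.2 names message support as one of its components, and Aim 1 opens with outreach, training and support together. Read that way, outcome 6 measures receipt of the whole program, which is a legitimate thing to report. This stands as a reason to keep such a composite if the investigators want it. It does not justify the label, or its use for Aim 1 item (2), which concerns self-directed training.

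It can also be said that low messaging should not be presumed, since screening (section 6.2) asks whether the caregiver already uses the portal to email the doctors. And section 6.8 has coaches log message frequency, so the parts could be reported separately in any case. Both points are fair. The first is why the table runs up to 90% messaging. The second makes the fix cheap, but the section 7.2.3 model would still use the composite.

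Three stronger readings are tempting and should not be drawn:

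- *Caregivers have only about two weeks to send the first message.* Section 6.7 could suggest this by placing the invitation at the end of the 6-week training. But section 6.1 lists messaging among the components offered, with no delayed start, and the first window in outcome 6 opens at baseline. The documents show an inconsistency about when messaging begins, not a two-week window.
- *The outcome measures need for help instead of training.* Modules and calls remain necessary conditions, so it measures both.
- *This is the trial's main feasibility figure.* It is the sixth of ten secondary outcomes, and no threshold or go/no-go decision is attached to it.

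**Conclusion.** The concern holds as a mismatch between name, aim and definition. Outcome 6 is labelled training completion and serves Aim 1 item (2), yet it counts as non-completers those caregivers who finish the modules and calls but miss either message window. Finishers who message in both windows are classified correctly.

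The direction is certain: relative to modules plus calls, the composite can only equal or lower the reported rate. The size is unknown, because it depends on messaging rates that the documents do not give. With 80% finishing and 70% of finishers messaging in each window, the reported rate would be 39% under independence and at most 56%. No row of the table is a forecast.

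The consequence is confined to a secondary feasibility outcome and its model. The burden analysis, its power and the intention-to-treat comparison are untouched. The change is worth making because it removes an ambiguity in a result meant to inform a later trial, and loses no information.

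**What to change.** 1. In section 3.2, outcome 6, define training completion as all six modules viewed plus at least three coach calls.
2. Use that definition in the section 7.2.3 model, and state it in the SAP, which is now silent on completion.
3. Report secure-message use separately for baseline to week 8 and for weeks 9 to 24, under Aim 1 item (1).
4. If a measure of engagement with the whole program is wanted, keep the present four-part composite alongside, under its own name.
5. Reconcile sections 6.1 and 6.7 on when messaging begins, so that the first window has a clear meaning.

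The cost is a short text change and one additional reported measure. The data are the same ones the present definition already needs.

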4 TRIAL DESIGN

We will conduct a parallel, two-arm pragmatic clinical trial comparing the intervention and attention control groups. The follow up period for the trial will be 6 months.

5 STUDY ENROLLMENT AND WITHDRAWAL

5.1 *Inclusion and Exclusion Criteria for Persons Living with Dementia*

The investigators will identify and recruit PLWD-CG dyads in which the PLWD has filled a new prescription for an antipsychotic medication. The study programmer will identify potential PLWD-CG dyads using an automated data algorithm that queries claims data and electronic health record (EHR) data on a weekly basis.

Because we will enroll dyads, there are inclusion/exclusion criteria for both persons living with dementia and their caregivers.

Persons with dementia inclusion criteria:

- Aged \geq 65 years
- Diagnosis of Alzheimer's Disease or related dementia (ADRD)
- Expected to live \geq 6 months from enrollment

Persons with dementia exclusion criteria:

- A diagnosis of bipolar disorder or schizopreniform disorder
- The primary care physician's opinion is that the person with dementia is expected to live less than 6 months.
- Primary language is not English (patient requires a translator).

5.2 *Inclusion and Exclusion Criteria for Caregiver Subjects*

Potentially eligible caregivers are identified by the family contact information in the electronic medical record.

Caregiver inclusion criteria:

- Aged \geq 21 years
- Lives with person with dementia or within 8 miles
- Provides at least 8 hours of care per week

Caregiver exclusion criteria:

- Diagnosis of Alzheimer's Disease or related disorders.
- Caregiver is not the spouse or adult child of the person living with dementia
- Primary language is not English (caregiver requires a translator).

5.3 ***Randomization Assignment Procedures***

5.3.1 ***Randomization Procedures***

The study biostatistician will create a randomization schedule and this will be uploaded into a REDCap database. Caregivers who remain eligible for the study after screening will be randomized within REDCap following the pre-set randomization schedule. All eligible caregiver-patient dyads will be block randomized to ensure comparable numbers of dyads enrolled in each study arm. Caregivers will be categorized according to age (<75 years, >=75 years), sex, and spouse/non-spouse.

R, an open-source statistical computing software, will be used to generate an even number of control and intervention assignments within each block.

5.3.2 ***Blinding***

Study staff will be blinded to study arm when verifying subject eligibility.

STAR Caregiver coaches interact with both intervention and control arm subjects. Group assignment is therefore known to these study staff. For the control group, coaches will conduct the consent process and orient participants to the printed and online materials available from the Alzheimer's Association.

The PI will remain blinded to arm assignment until follow-up is complete. Only the study biostatistician, programmer, and project manager will be un-blinded to arm when preparing reports for the Safety Officer. The PI will be un-blinded for reporting any serious adverse events or incidental deaths to the Safety Officer and NIA staff, should such events occur during the course of the trial.

5.4 ***Withdrawal***

Caregivers are free to withdraw from study activities at any time. However, we will still measure antipsychotic medication utilization rates between intervention and control. A waiver of consent to access PLWD medical records after withdrawal will be obtained.

5.5 ***Control arm***

We will use an attention control arm. PLWD-Caregiver dyads randomized to the control arm will receive paper-based information from the Alzheimer's Association and National Institute on Aging including links to online training resources. Control arm participants will also receive 3 scripted secure messages (one at 4 weeks, one at 8 weeks and one at 6 months following randomization) to remind them to read the provided materials, check the provided web links to training resources, and check in with their primary care physician if they have concerns about the PLWD.

